4.3.2 Treatment Failures

Treatment failures will be offered SOC therapy.

4.3.3 Subject Replacement Policy

Subjects withdrawn from the study for any reasons will not be replaced.

4.4 Assignment of Subjects to Treatment Groups

The Investigator will enter a unique identifier of each subject in both the eCRF and the confidential subject identification list. The randomization numbers will be allocated sequentially in the order in which the subjects are enrolled. The Investigator will inform the monitor of new subjects enrolled.

Subjects who withdraw from the study or complete the study are not permitted to re-enroll.

4.5 Relevant Protocol Deviations

In case of any major protocol deviation, the Investigator and Octapharma will decide on the further participation of the subject in this study after having discussed all relevant aspects.

A list of all included subjects with all deviations from the intended study procedures and other criteria that may affect the validity of subject data for statistical analysis will be prepared after the clinical phase of the study is completed. The list will be discussed prior to study unblinding by a panel consisting of the clinical study manager, a medical expert of the Sponsor, the data manager, and the study statistician. This panel will decide upon the inclusion of each subject in the analysis populations.

4.6 Subsequent Therapy

If a subject decides to withdraw from the study or is withdrawn by the Investigator, she/he will continue to receive SOC therapy.

Property of Octapharma. Do not copy or distribute without written permission

5 INVESTIGATIONAL MEDICINAL PRODUCT(S)

5.1 Characterization of Investigational Product(s)

Octagam is a 10% IVIG ready for intravenous administration. *Octagam 10%* is produced from a pool of at least 1000 donations of human fresh frozen plasma per batch. The large donor pool ensures that the product contains a broad range of antibodies directed against pathogens and foreign antigens, which is far more diverse than that of plasma from an individual donor. Donor plasma sampling, the manufacturing of the product and the measures to ensure the product's viral safety are subject to strict regulations laid down by regulatory authorities. Octapharma exclusively uses plasma which has been tested by nucleic acid testing techniques.

During the manufacturing process of *Octagam 10%*, significant viral reduction is obtained via a combination of 3 validated manufacturing steps: cold-ethanol fractionation, solvent/detergent treatment with tri-n-butyl phosphate and Octoxynol (Triton X100), and pH 4 treatment. The efficacy of the virus inactivation procedures has been extensively validated according to relevant international guidelines. The composition with the most important ingredients and the biochemical characteristics are summarized in the Investigators' Brochure (IB).

For placebo, saline for intravenous infusion will be used.

5.2 Packaging and Labelling

5.2.1 For the US sites

Octagam 10% delivered as ready-to-use solution in glass bottles; commercially labeled product will be provided to the clinical study sites. Appropriately trained study staff may over-label the commercial supplies with an investigational product label, provided by the Sponsor, that will meet all FDA requirements under 21 CFR 312.6 and shall include the statement: **Caution: New Drug—Limited by Federal (or United States) law to investigational use**, as permitted in accordance with local Standard Operating Procedures (SOPs). Investigational product labels will also be provided for placebo supplies that will be sourced from the site pharmacy's commercial supplies.

After transfer and pooling into Polyvinyl Chloride-free, Diethylhexylphthalate-free and latex-free, infusion bags, the medication (*Octagam 10%* or placebo) will be blinded with an over pouch and re-labeled (both the infusion bag [as permitted in accordance with local SOPs] and the over pouch). The over-label for the infusion bags and over pouches will also include the 21 CFR 312.6 required statement: **Caution: New Drug—Limited by Federal (or United States) law to investigational use**.

Instructions for over-labeling both *Octagam 10%* and saline with investigational product labels will be provided in a study-specific pharmacy manual.

US Master Label – Octagam 10%:

Caution: New Drug-Limited by Federal (or United States) law to investigational use	
Study: GAM10-10	
Octagam 10%	Unit size: _____ mL
1 mL contains: 100 mg protein of which 96% is human normal immunoglobulin. Infusion solution for intravenous administration.	
To be stored at +2°C (36°F) to +8°C (46°F) and protected from light. Must not be frozen. Must be inspected visually for particulate matter and discoloration prior to administration. Do not use non-homogenous solutions or those that have a deposit.	
To be warmed up to room or body temperature before use.	
Dosage: refer to Clinical Study Protocol, Section 5.4	
Patient no.: _ _ _ _ _ _ _ _	Visit no.: _ _ _
Infusion Day: _ _ _	
Sponsor: Octapharma USA, INC. [name] [REDACTED]	
[REDACTED]	
Batch no.: _____	Expiration date: _____

US Master Label – Saline:

Caution: New Drug-Limited by Federal (or United States) law to investigational use	
Study: GAM10-10	
Sodium Chloride 0.9% w/v solution	Unit size: _____ mL
Sterile solution for intravenous infusion 1000 mL of solution contain Sodium chloride 9.00 g	
Electrolyte concentrations mmol per 1000 mL (approx):	
Sodium	154 mmol
Chloride	154 mmol
Do not store above +25°C (+77°F) [depending on product purchased]	
Only to be used if solution is clear and container undamaged	
Dosage: refer to Clinical Study Protocol, Section 5.4	
Sponsor: Octapharma USA, INC. [name] [REDACTED]	
[REDACTED]	
Batch no.: _____	Expiration date: _____

US Master Label – Blinded label for infusion bags and over pouch:

Caution: New Drug-Limited by Federal (or United States) law to investigational use		
Study: GAM10-10		
Octagam 10% OR Sodium Chloride 0.9% w/v solution	Unit size: _____ mL	
1 mL contains either 100 mg protein of which 96% is human normal immunoglobulin OR sodium chloride 0.9% w/v solution.		
Infusion solution for intravenous administration.		
Patient no.: _ _ _ _ _ _ _ _	Visit no.: _ _ _	Infusion Day: _ _ _
Investigator: _____		
Date and time of preparation: _____		
If not infused immediately, to be stored at +2°C (36°F) to +8°C (46°F) until		
Expiration date and time: _____		
Must not be frozen.		
To be warmed up to room or body temperature before use.		
Sponsor: Octapharma USA, INC. [name] [REDACTED]		
[REDACTED]		

5.2.2 For the Russia and Ukraine Sites

Octagam 10% will be delivered as ready-to-use solution in glass bottles; labeled and packed as clinical kits will be provided to the clinical study sites.

Marketed saline solution for intravenous infusion, that can be used in the respective countries, will be purchased by Sponsor or designee and provided to the local pharmacies or sites. Saline should be stored and transported at +0°C to 30°C.

Instructions for over-labeling both *Octagam 10%* and saline with investigational product labels will be provided in a study-specific pharmacy manual.

After transfer and pooling into Polyvinyl Chloride-free, Diethylhexylphthalate-free and latex-free, infusion bags, the medication (*Octagam 10%* or placebo) will be blinded with an overpouch and blinded labels will be applied on the infusion bag and the overpouch.

EU Master Label – Octagam 10%:

FOR CLINICAL TRIAL USE ONLY	Study: GAM10-10
Octagam 10%	Unit size: _____ mL
1 mL contains: 100 mg protein of which $\geq 95\%$ is human normal immunoglobulin. Infusion solution for intravenous administration.	
To be stored at +2°C to +8°C and protected from light. Must not be frozen.	
Must be inspected visually for particulate matter and discoloration prior to administration. Do not use non-homogenous solutions or those that have a deposit.	
To be warmed up to room or body temperature before use.	
Dosage: refer to Clinical Study Protocol, Section 5.4	
Patient No.: _____	Visit Day.: _____
Investigator: _____	
Sponsor: Octapharma USA, INC. [name] [REDACTED]	
Batch no.: _____	Expiration date: _____

EU Master Label – Saline:

FOR CLINICAL TRIAL USE ONLY	Study: GAM10-10
Sodium Chloride 0.9% w/v solution	Unit size: _____ mL
Sterile solution for intravenous infusion	
1000 mL of solution contain	
Sodium chloride 9.00 g	
Electrolyte concentrations mmol per 1000 mL (approx):	
Sodium	154 mmol
Chloride	154 mmol
To store this product below 30°C. Do not freeze.	
Only to be used if solution is clear and container undamaged	
Dosage: refer to Clinical Study Protocol, Section 5.4	
Patient No.: _____	Visit Day.: _____
Investigator: _____	
Sponsor: Octapharma USA, INC. [name] [REDACTED]	
Batch no.: _____	Expiration date: _____

EU Master Label – Blinded label for infusion bags and over pouch:

FOR CLINICAL TRIAL USE ONLY	Study: GAM10-10
Octagam 10% OR Sodium Chloride 0.9% w/v solution	Volume: _____ mL
1 mL contains: 100 mg protein of which $\geq 95\%$ is human normal immunoglobulin OR sodium chloride 0.9% w/v solution.	
Infusion solution for intravenous administration.	
To be stored at +2°C to +25°C. Must not be frozen.	
To be warmed up to room temperature before use.	
Dosage: see study protocol Section 5.4	
Patient No: _____	Visit Day.: _____
Bag number: ___ of ___	
Date and time of preparation: _____	
Infusion to be completed latest by (Date and time): _____	
Investigator: _____	
Any unused solution residues or waste material to be disposed according to local requirements at the study site.	
Sponsor: Octapharma USA, INC. [name] [REDACTED]	

5.3 Conditions for Storage and Use

Octagam 10% should be stored and transported light-protected at +2°C to +8°C (36°F to 46°F) and must not be frozen. *Octagam 10%* must not be used after its expiration date.

Saline should be stored and transported according to its product information. Storage conditions will be stated on the IMP label.

The authorized personnel at the individual pharmacies will ensure that the IMP is stored in appropriate conditions with restricted access and in compliance with national regulations.

5.4 Dose and Dosing Schedule

Octagam 10% is available in glass bottles with different volumes of human immunoglobulin. Glass bottles of different volume should be combined in order to reach the required amount of IgG.

Octagam 10% or placebo will be administered by intravenous infusions on 4 consecutive days. The amount of *Octagam 10%* calculated on the dosage delivery schedule is 2 g/kg divided evenly over 4 days (0.5 g/kg/day).

If a subject is randomized to receive placebo, the same volume with the same infusion rate as would have been applied in case the subject would have been randomized to

2.0 g/kg *Octagam 10%* will be used. Therefore, they will receive an equal dose of placebo given over 4 days.

Body weight is to be measured at Screening or within 24 hours of first IMP administration and reported to the pharmacist or designee as it is needed for the preparation of the following study medication dosages.

All subjects should be clinically assessed for being adequately hydrated prior to IMP administration. TEE prophylaxis should be considered.

The initial infusion rate for each infusion episode will be:

- 0.01 mL/kg/min (60 mg/kg/h) for the first 30 minutes (\pm 5 minutes)
- if tolerated, advanced to 0.02 mL/kg/min (120 mg/kg/h) for the next 30 minutes (\pm 5 minutes)
- if tolerated, advanced to 0.04 mL/kg/min (240 mg/kg/h) for the remainder of the infusion

The interval of 30 minutes may be prolonged as per discretion of the investigator.

In subjects at risk for thromboembolic adverse reactions and acute renal failure (such as advanced age, hypertension, history of thrombotic episodes, subjects with prolonged periods of immobilization, concomitant nephrotoxic medication, diabetes mellitus, overweight, hypovolemia), *Octagam 10%* should be administered at the minimum rate of infusion practicable.

If AEs occur during the infusion, the rate is to be reduced to half the rate at which the event occurred, or the infusion is to be interrupted until symptoms subside. The infusion may then be resumed at a rate tolerated by the subject. In case of severe hypersensitivity or anaphylaxis, the infusion will not be restarted and all treatment with the IMP will be withdrawn. The subject will continue to be followed up in accordance with study-specific procedures as specified in the protocol with the exception that no further administrations of IMP will be performed. The subject will receive ongoing treatment in accordance with local SOC.

Events that will prevent the scheduled administration of study drug will include but not limited to:

- Uncontrolled blood pressure elevation (ie, systolic is \geq 160 mmHg or diastolic is \geq 90 mmHg)
- Chest pain with or without electrocardiogram changes
- Thrombotic events
- New onset seizures

- Acute Kidney Injury (AKI) as defined by KDIGO Clinical Practice Guideline for AKI as any of the following:
 - Increase in serum creatinine by ≥ 0.3 mg/dl (≥ 26.5 $\mu\text{mol/l}$) within 48 hours
 - or Increase in serum creatinine to ≥ 1.5 times baseline, which is known or presumed to have occurred within the prior 7 days
 - or Urine volume < 0.5 ml/kg/h for 6 hours
- Stroke
- Myocardial infarction.

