 - Kidney failure (G5): GFR <15 ml/min/1.73 m²
7. Currently requiring IMV or having received IMV during the last 30 days
8. Known clinically significant preexisting lung, heart, or neuromuscular disease that, in the investigator's opinion, would impact subject's ability to complete study or may confound the study results
9. Body weight >125 kg
10. Women who are pregnant or breast-feeding
11. Subjects who received COVID-19 convalescent plasma, IVIG products, anti-interleukin agents (eg, Tocilizumab), or interferons for their COVID-19 disease before enrollment or plan to receive this treatment during the course of the study
12. Enrolled in other experimental interventional studies or taking experimental medications (ie, convalescent plasma). Diagnostic studies can be allowed if the anticipated total blood volume to be drawn across both studies and for therapeutic purposes does not exceed 450 mL over any 8-week period.

Test Product, Dose, and Mode of Administration:

Octagam 10%, 2 g/kg divided by 4 days (0.5 g/kg/day), administered by intravenous infusion over approximately 2 hours per day over 4 consecutive days.

Duration of Treatment:

The duration of treatment is 4 days. The duration of the entire study for each subject will be approximately 33 days:

- Screening period: 1 day
- Treatment period: 4 days

Name of Sponsor/Company: Octapharma USA	
Name of Investigational Product: Octagam [®] 10%	Protocol Identification Code: GAM10-10
Name of Active Ingredient: Intravenously Administered Immunoglobulin	Date of Final Protocol: 27-January-2021

- Follow-up period: 29 days

Reference Therapy, Dose, Mode of Administration:

Placebo (saline), equivalent volume as test product, administered by intravenous infusion over approximately 2 hours per day over 4 consecutive days.

Efficacy Parameters:

Efficacy assessments include clinical status, oxygenation and ventilator status, SARS-CoV-2 RT-PCR results, oxygen saturation, modified Borg Dyspnea Scale and MQoL-SIS.

Safety Parameters:

Safety assessments include AEs and SAEs, vital signs including SpO₂, clinical laboratory evaluations and chest CT/chest X-ray findings.

Study Procedures:

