3.1.4 Overall Study Design and Plan

This is a randomized, double-blind, placebo-controlled, multicenter, two-arm adaptive Phase 3 study designed to evaluate if high-dose *Octagam 10%* therapy can stabilize or improve clinical status in subjects with severe COVID-19.

Following Screening procedures, subjects that meet eligibility criteria will be randomized to receive either *Octagam 10%* in a dose of 2 g/kg over 4 days (0.5 g/kg/day), or an equivalent volume of placebo (saline). The infusion will be

administered over a period of 2 hours per day over a total of 4 consecutive days. The first dosing will take place within 24 hours of the Screening Visit.

Approximately 208 male or female adult subjects will be recruited so that approximately 104 subjects in each treatment arm will complete the study. Each subject's participation will last a total of approximately 33 days, including 29 days for safety follow-up, followed by a one-year registry follow-up.

This study is planned to start in Q2 2020 and to be completed by Q4 2020, resulting in a maximal overall duration of 7 months. The planned follow-up registry will begin in Q3 2020 and to be completed in Q4 2021.

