The subject will receive either *Octagam 10%* medication in the dose of 2 g/kg administered over 4 days (0.5 g/kg/day), or an equivalent volume of placebo (saline), infused slowly over approximately 2 hours per day over 4 consecutive days. Note: Subjects must be monitored before infusion and carefully observed for any symptoms at least once throughout the infusion period and at least 1 hour thereafter.

The following activities/assessments will be performed on **Day 1 through Day 4**:

1. Infusion of IMP according to randomization code: *Octagam 10%* or placebo
2. Vital signs (taken once during and again after infusion)
3. SpO₂ saturation (see Section 7.2.4)
4. Post-infusion site assessment
5. Modified Borg Dyspnea Scale
6. MQoL-SIS
7. AE monitoring
8. Concomitant medication use review and documentation

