## **3. Study Design, Procedures, and Analysis Timing**

This is a randomized, double-blind, placebo-controlled, multicenter, Phase 3 study in the US, Russia and Ukraine to evaluate whether high-dose Octagam 10% therapy can stabilize or improve clinical status in subjects with severe COVID-19 disease.

Following screening procedures, eligible subjects will be randomized in a 1:1 ratio to receive either Octagam 10% in a dose of 2 g/kg over 4 days (0.5 g/kg/day), or an equivalent volume of saline (placebo).

The infusion will be administered over a period of 2 hours per day over a total of 4 consecutive days. The first dosing will take place within 24 hours of the Screening Visit.

Approximately 208 male or female adult subjects will be recruited so that approximately 104 subjects in each treatment arm will complete the study. Each subject's participation will last a total of approximately 33 days, including 29 days for safety follow-up, followed by a one-year registry follow-up.

The final primary analysis will take place after database lock.

The primary analysis may also be conducted prior to database lock but after the last subject enrolled completes their Day 33 visit (or discontinues). If conducted, this analysis would be distributed to a limited unblinded team to evaluate the need to submit an emergency use application. Full details on this process will be provided in an unblinding plan and the clinical study report.

Upon end of study follow up, an end of study analysis may be conducted.

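### The 2-hour daily infusion stated in Protocol 3.1.4 and SAP 3 cannot be met under the dose and rates in Protocol 5.4, which take 162.5 minutes

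*Protocol*

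**What the plan says.** Five places give a duration for the daily infusion. Two state it without qualification:

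- Protocol 3.1.4 (overall design): "administered over a period of 2 hours per day over a total of 4 consecutive days".
- SAP 3 (study design) repeats it: "The infusion will be administered over a period of 2 hours per day over a total of 4 consecutive days".

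Three qualify it:

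- Protocol synopsis, test product and reference therapy: "administered by intravenous infusion over approximately 2 hours per day over 4 consecutive days".
- Protocol synopsis, infusion visits, in the same terms as 6.1.2.
- Protocol 6.1.2, the instruction for the Day 1 to Day 4 visits: "infused slowly over approximately 2 hours per day over 4 consecutive days".

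Protocol 5.4 states no duration. It sets the daily dose at 0.5 g/kg and gives the rates for every infusion:

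- "0.01 mL/kg/min (60 mg/kg/h) for the first 30 minutes"
- "if tolerated, advanced to 0.02 mL/kg/min (120 mg/kg/h) for the next 30 minutes"
- "if tolerated, advanced to 0.04 mL/kg/min (240 mg/kg/h) for the remainder of the infusion"

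Each of the first two steps has a tolerance of 5 minutes either way. Section 5.4 also says: "The interval of 30 minutes may be prolonged as per discretion of the investigator". It tells sites to use the slowest workable rate in subjects at risk of thromboembolism or renal failure, and to halve the rate or interrupt the infusion if an adverse event occurs. Placebo is given at the same volume and rate.

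**The concern.** Dose, rate and duration are tied together: once two are fixed, the third follows. Section 5.4 fixes the dose and the rates, so it also fixes the duration, and that duration is not the one stated elsewhere.

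Sites therefore hold two administration statements that cannot both be followed. The one in 6.1.2 is not background text. It is the visit instruction for the infusion days, and it puts the 2-hour figure beside the dose. Nothing in the documents says which statement prevails.

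The direction of the mismatch matters. Finishing in 2 hours implies a faster average rate than 5.4 allows, and Protocol 1.2 says that adverse events with intravenous immunoglobulin become more frequent as the infusion rate rises and that recommended rates should be respected. There is also a practical side. Protocol 5.5 and 6.1.2 require observation during the infusion and for at least an hour afterwards, so a visit planned around 2 hours is about 40 minutes short.

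**Working it through.** **Inputs**

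| Quantity | Value | Source |
|---|---|---|
| Daily dose | 500 mg/kg | Protocol 5.4 |
| Concentration | 100 mg/mL | Product labels, Protocol 5.2 |
| Step 1 | 0.01 mL/kg/min for 30 min (±5) | Protocol 5.4 |
| Step 2 | 0.02 mL/kg/min for 30 min (±5) | Protocol 5.4 |
| Step 3 | 0.04 mL/kg/min for the rest | Protocol 5.4 |
| Stated duration | 120 min | Protocol 3.1.4, SAP 3 |

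**Concentration check.** At 100 mg/mL, 0.01 mL/kg/min is 0.01 × 100 × 60 = 60 mg/kg/h. Likewise 0.02 gives 120 and 0.04 gives 240. These match the equivalents printed in 5.4, so 5.4 itself confirms the concentration.

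**Daily volume.** 500 / 100 = 5 mL/kg.

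**Can the stated 120 minutes be reproduced?** It needs an average of 5 / 120 = 0.0417 mL/kg/min, or 500 / 2 = 250 mg/kg/h. The highest listed rate is 240 mg/kg/h, so the required average is 4.2% above the maximum. At that maximum from the first minute, the infusion takes 5 / 0.04 = 125 min. After the two opening steps, the remaining 4.1 mL/kg would have to run in 60 min, at 4.1 / 60 = 0.068 mL/kg/min, a rate 5.4 does not list. The stated figure cannot be reproduced.

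**Duration under 5.4.** With step 1 lasting *a* minutes and step 2 lasting *b* minutes:

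T = a + b + (5 − 0.01a − 0.02b) / 0.04 = 125 + 0.75a + 0.5b

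| a, b (min) | T (min) | Against 120 min |
|---|---|---|
| 30, 30 (nominal) | 162.5 | +35% |
| 25, 25 (shortest within tolerance) | 156.25 | +30% |
| 25, 35 | 161.25 | +34% |
| 35, 25 | 163.75 | +36% |
| 35, 35 (longest within tolerance) | 168.75 | +41% |

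The same check in milligrams: step 1 gives 30 mg/kg and step 2 gives 60 mg/kg. The remaining 410 mg/kg at 240 mg/kg/h takes 60 × 410 / 240 = 102.5 min, and 30 + 30 + 102.5 = 162.5 min. The average rate under the nominal steps is 500 / (162.5 / 60) = 184.6 mg/kg/h.

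**Sensitivity to how the dose is counted.** If the 500 mg/kg is read as immunoglobulin at 96% of total protein (the US label figure), the volume is 500 / 96 = 5.21 mL/kg. The nominal time becomes 167.7 min and the time at the highest rate 130.2 min. This reading widens the gap.

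**The case against.** The strongest reply is that duration is an outcome of tolerability here, not a target. Section 5.4 is the only place with rates, steps and tolerances, and it gives no duration. All the labels except the US blinded one send sites to 5.4 for dosage. Three of the five duration statements are qualified, including the visit instruction. The two unqualified ones are design summaries, and may simply have dropped the qualifier. Nothing tells a site to exceed a listed rate. The only hard completion limit, 8 hours after preparation in Protocol 5.5, leaves ample room for 168.75 minutes. The 125-minute figure describes a schedule 5.4 does not permit, and would itself pass as about 2 hours.

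Much of this stands. The label references reduce the risk that a site works from the wrong statement. The 125-minute figure shows only that exactly 2 hours is out of reach; the practical comparison is 162.5 minutes with 2 hours. The arms share one schedule, the per-protocol population counts dose received and completed infusions rather than minutes, and no analysis uses infusion time.

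What does not stand is the appeal to the qualifier. It is absent from Protocol 3.1.4 and SAP 3. Where it does appear, no tolerance is defined, and the shortest schedule within the step tolerances is already 30% over. Nor does the flexibility in 5.4 help: prolonging steps, slowing the rate for at-risk subjects, and halving or interrupting for adverse events all lengthen the infusion.

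**Conclusion.** The concern holds. On the protocol's own dose, concentration and rates, a daily infusion takes 162.5 minutes nominally and 156.25 to 168.75 minutes within the step tolerances. That is 30% to 41% longer than the stated 2 hours, which no rate listed in 5.4 can achieve.

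The contradiction is firm against Protocol 3.1.4 and SAP 3. Against the synopsis and Protocol 6.1.2 it depends on how loosely the qualifier is read, but a gap of at least 30% is not a reasonable reading of it.

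The result rests on the 100 mg/mL concentration, which the labels and the rate equivalents in 5.4 both support, and on an infusion that proceeds without slowing or interruption. The consequence is limited to the consistency of administration and safety instructions. No under-dosing, bias between arms, or effect on any endpoint, power or type I error is claimed.

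**What to change.** Reconcile the following so that the dose, rate steps and daily infusion time agree arithmetically:

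- Protocol synopsis (test product, reference therapy, and infusion visits)
- Protocol 3.1.4
- Protocol 5.4
- Protocol 6.1.2
- SAP 3

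Which element changes is a clinical decision for the sponsor, and none is proposed here. If a qualified duration is kept anywhere, the text should say what range it covers.

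The cost is a text edit in the protocol and one sentence in the SAP. No planned endpoint, test, analysis population or sample size needs to change.
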